#### Expected results:

We anticipate that the  $K_{trans}$  and

the size of the plaques (vessel wall area) will change in a favorable way over the time course of the study due to institution of treatment (medicines and life style modification). We anticipate that changes in the vessel wall (plaque and vessel wall remodeling) as measured by high-resolution MRI will change in a way that is predicted by the change in the DCE-MRI inflammation parameters but that changes in the DCE-MRI inflammation parameters will precede those of the morphological changes. We expect this because previous studies have shown changes in inflammatory cell content occur within three months of the initiation of statin therapy, whereas changes in plaque morphology as measured by high-resolution anatomical

MRI occur at approximately twelve to eighteen months following the initiation of statin therapy (19, 41, 42).

A # 2: To investigate the relation between direct measures of plaque inflammation (MRI) and indirect measures of inflammation (blood serum markers of inflammation, Echocardiographic and CT studies) as therapy progresses.

Rationale: DCE-MRI studies have shown a correlation between the number of macrophages and amount of neovasculature and the patterns of dynamic contrast enhancement (42, 43). Our hypothesis is that over a longer period of time (36 months); there would be a correlation between these two (direct and indirect measures of inflammation).

Data analysis: The DCE-MRI dynamic enhancement parameters (Ktrans and  $\square_p$ ) will be determined as described in section SA # 3 above. Samples will be drawn for serum markers of inflammation (hsCRP, LpPLA2, IL-6). Relationship if any between the inflammation within the plaque and serum markers will be observed.

Expected results: We expect a predictable correlation between the inflammatory markers in the blood and inflammation present within the vessel wall/plaque seen on the initial and post treatment sampling; this expectation is based on prior literature (19, 22, 46, 47).

We will carry out the modeling using SAS/STAT procedure MIXED.

A # 4: To determine the efficacy of comprehensive treatment (life style modification + statin) versus life style modification alone.

Rationale: The effects and efficacy of various combinations of treatment have not been studied in the context of radiation vasculopathy and accelerated atherosclerosis.

Data analysis: The techniques described in sections above (A1 to A3) would be used in combination to determine plaque-remodeling, inflammation within the plaque and serum markers of inflammation and compare efficacy of different treatment regimens. Each patient will get MRI examinations before and after treatment and therefore patients will serve as their own control.

Expected results: We anticipate that the efficacy of comprehensive treatment would outperform the results obtained with life style modification alone.

We will carry out the modeling using SAS/STAT procedure MIXED.

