### **Inclusion criterion:**

Age 22 and above with prior head and neck or chest irradiation, six months or more post head and neck irradiation, documented subclinical cardiovascular disease (inflammatory markers in the serum, pre-existing plaques [detected by ultrasound, CT or MRI], asymptomatic major arterial stenosis, and not being considered for arterial surgery or endovascular treatment.

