#### **Examination Plan Overview:**

All participants will be given IRB approved informed consent. Those who decide to take part and give consent for the study would be enrolled in the research study. We would be taking snap shots with MRI at three data points and monitor treatment effects. Overview of the research study is shown in Fig 2. A baseline MRI will be performed to assess arterial atherosclerotic constituents. Once the initial MRI has been performed, and in the case where subclinical disease is present i.e. elevated blood markers or arterial plaque on MRI. HNXRT cancer survivor patient with abnormal tests will be started on treatment, which includes life style modification and-/or lipid lowering medication. Patients with positive tests would be divided randomly into two groups; one group will receive life style modification + statin therapy and the second group will receive life style modification alone. A repeat MRI and blood tests (2nd study) will be performed at 18 months after initiation of such treatment to assess changes in plaque morphology and enhancement characteristics. MRI findings of baseline and final would be

correlated with surrogate markers of inflammation, Echo and CT findings. A final set of MRI and blood tests will be performed at 36 months after initiation of such treatment to assess changes in plaque morphology and enhancement characteristics. MRI findings of baseline and final would be correlated with surrogate markers of inflammation, Echo and CT findings.

Fig 2. Shows overview of the research study

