#### Treatment and Clinical Follow-Up:

Patients enrolled in the “Accelerated Atherosclerosis in High Risk Population Groups: An Assessment by Magnetic Resonance Imaging” study will be evaluated in the cardiology clinic by [name],

FACC, FSCAI who is the Director of Peripheral Vascular Intervention at Emory University and treats patients with carotid artery disease. All these patients will be randomized based on the last digit of their medical record number. If the last digit will be an even number they will then be given a statin, which they will take and will also be instructed about regular exercise. Patients will be made aware of the side effects of statins and about the procedures to report these side effects. Patients with the last digit being an odd number will ONLY be advised about exercise. All patients will have regular visits and patients on a statin will be followed up and evaluated for any adverse effects of the medication and for compliance at 18 and 36 months by the study preventive cardiologist. The preventive cardiologist or any other physician involved with care of the patient may elect for more frequent follow up as well as modification or discontinuation of the study prescribed therapy if deemed necessary based on his or her best clinical judgment.

These patients will get routine clinical follow-up in the oncology (The Winship Cancer Institute Clinics) and cardiology clinics (Emory Hospital) as part of the ongoing routine clinical care.

Within five weeks of initial MRI evaluation, our recruited research that demonstrate increased blood markers and/or atherosclerosis on MRI would be subjected to life style modification ± medical (statin) therapy. Department of Cardiology would prescribe and monitor statin therapy: Rosuva (20 mg once a day) with target LDL goal < 70; non-HDL goal < 100 and Aspirin (81 mg once a day). The rational for using rosuva 20 mg is because this dosage has already been successfully used in JUPITER Trial (35). The follow-up by Cardiology department would comprise educating the patients on life style modification and also how to monitor and report any adverse drug affects which if expected would be further assessed with laboratory testing with LFT's and CBC. Any patients who suffer clinical side effects of treatment as part of our research would be taken off our study. Patients will continue to follow-up in the survivorship clinic and with the preventative cardiologist as indicated.

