### **MRI Examination:**

Pre-MRI screening and informed consent:

Upon arrival at the MRI Research Center, a trained MRI technologist will screen each study participant for metal objects and implants that may be hazardous in the MRI environment. The subject will be given a copy of the informed consent form. The PI or the co-investigator will be responsible for ensuring that the subject fully understands the procedure, for answering any questions the subject may have and for obtaining written informed consent. The technologist will then guide the subject to the MRI scanner room.

Imaging protocol:

All scans will be performed on a 3.0T MRI scanning system using 4-channel dedicated coil. A fast gradient echo 3-plane localizer will be performed to locate the major artery and its bifurcations. The location and extent of the lesion will be ascertained or verified from the 3D-TOF angiographic images (described below). The site of imaging will be selected to coincide with the location of a selected known lesion. The acquired axial images and the MIP formatted images will both be used to verify the region of stenosis and will be used to prescribe the high-resolution anatomical images (described below). Five to ten imaging locations will be prescribed depending on the known extent of the lesion. Double-oblique sections will be acquired for optimal visualization of the artery plaques for all the sequences described below.

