Statistical analysis: The three parameters mentioned above (Ktrans,  $\square_p$ , vessel wall) continuous variables. Before performing the statistical modeling we will check first to see if the distributions of these variables are normal; otherwise, we will use log transformation prior to the modeling of these parameters. We will first compute the mean, median, and standard deviation at each time point for these parameters. We will plot these data by patient over the 3 time points to examine the longitudinal profiles. We will use the linear mixed effects model (random coefficient model with random intercept and slope) with these parameters serving as dependent variables. The independent variables will be the time indicator and other potential confounders that we may need to control (e.g. age, gender, race, and body mass index). The interest in this model is the coefficient associated with the time indicator, which allows us to obtain the adjusted population mean estimate of these parameters at each of these time points. Since we have the best linear unbiased prediction estimates of the random intercepts and slopes for each subject,

we will be able to examine individual subject profiles and assess the temporal trend for each subject. Thus this random coefficient linear mixed effects model will allow us to obtain the overall adjusted mean estimate ( $K_{trans}$ ),

for each of the individual subjects, overall across all above mentioned time points, and at each of the time points.

To assess the association between the vessel wall area, and  $K_{trans}$  and

linear mixed effects models (random coefficient models) to obtain the estimates of fixed effects.

We will carry out 2 analyses in these models, we will use vessel wall area as the dependent variable and  $K_{trans}$  and

potential confounders if necessary. The slope estimate from these models is interpreted as a measure of adjusted association between the changes in plaque size and morphology, and DCE-MRI dynamic enhancement parameters.

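### Aim 3 credits the pooled change over time to treatment, but an uncontrolled before-after change in patients selected for disease cannot support that attribution

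*Combined protocol and SAP*

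**What the plan says.** All references are to the combined protocol and SAP.

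- **Model.** The Aim 3 statistical analysis (Specific Aims, A # 3) fits a random-intercept, random-slope mixed model to Ktrans, a second DCE parameter and vessel wall area. "The independent variables will be the time indicator and other potential confounders that we may need to control"; the examples given are age, gender, race and body mass index. "The interest in this model is the coefficient associated with the time indicator". Arm is not named, alone or with time.
- **Attribution.** The expected results for A # 3 say that these measures "will change in a favorable way over the time course of the study due to institution of treatment", taking medicines and lifestyle modification together. The Project Timeline also describes the changes as related to therapy.
- **Comparator.** The A # 4 data analysis refers back to the Aim 1 to 3 techniques and treats each patient as his or her own comparator. Under Examination Plan Overview both randomised groups receive lifestyle modification, and one adds a statin.
- **Patient selection.** Entry requires "documented subclinical cardiovascular disease (inflammatory markers in the serum, pre-existing plaques [detected by ultrasound, CT or MRI" or asymptomatic stenosis (Inclusion criterion). Treatment starts "in the case where subclinical disease is present i.e. elevated blood markers or arterial plaque on MRI". Treatment and Clinical Follow-Up repeats the rule for patients "that demonstrate increased blood markers and/or atherosclerosis on MRI would be subjected to life style modification".
- **Site selection.** "The site of imaging will be selected to coincide with the location of a selected known lesion" (MRI Examination, Imaging protocol).

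**The concern.** A before-after change measures a treatment effect only if the outcome would otherwise have stayed put. Three things can move it here without any treatment effect.

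- **Regression to the mean.** Blood is drawn immediately before each MRI (Variables and Measures), so the sample that qualifies a patient may also be the analysis baseline. A value picked for being high tends to be lower on repeat.
- **Natural progression.** The Introduction describes accelerated atherosclerosis in this population, which would push the other way.
- **Measurement drift.** Three scans over 36 months can differ for technical reasons.

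The pooled time coefficient cannot separate these from treatment. At stake is a report that treatment improved plaque inflammation or morphology, resting on a change that may have another cause, or a real benefit hidden by progression.

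**Working it through.** **1. What the plan powered.** Sample Size assumes f = 0.28 over three measurements, 92 subjects and alpha 0.05. For a one-way ANOVA with 92 per time point, the noncentrality is 3 × 92 × 0.28² = 21.64 and power is 0.990, which reproduces the plan's figure. In SD units, f = 0.28 is a change of 0.28 × 3/√2 = 0.59 if reached by 18 months and held, or 0.28 × √6 = 0.69 if linear over 36 months. This calculation concerns change over time, with no arm contrast in it.

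**2. Regression to the mean in a marker used for selection.** The documents give neither a reliability nor a cut-off for a raised marker. Assumptions:

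- reliability ρ of 0.6 to 0.8
- raised means the upper half of a normal distribution
- plaque present with probability p, independent of the marker
- no true effect or trend
- n = 90 (100 less about 10% attrition)

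Patients qualify by marker or plaque. Those who qualify by plaque with a low marker drift upward and offset the fall. The mean baseline excess among those selected is

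m = 0.798 × (1 − p)/(1 + p),

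the expected fall is (1 − ρ)m, and the SD of change is √[(1 − ρ)²(1 − m²) + 1 − ρ²]. The chance of a significant improvement then follows from a noncentral t with noncentrality fall/SD × √90. Nominal is 2.5% in the favourable direction. Results for ρ = 0.6, 0.7, 0.8:

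- p = 0.5: m = 0.266; fall 0.106, 0.080, 0.053 SD; false improvement 20%, 16%, 12%.
- p = 0.8: m = 0.089; fall 0.035, 0.027, 0.018 SD; false improvement 5.6%, 5.1%, 4.5%.
- p = 1: m = 0; no fall; 2.5%.

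Other simulations of this set-up gave 12% to 18% and 5% to 7% for the first two rows, so only the rough size should be read. Every fall is well below the planned 0.59 to 0.69 SD.

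**3. The outcomes Aim 3 actually models.** These are MRI measures. If patients are selected on a serum marker alone, the expected fall in an MRI measure is e(1 − ρ)m, where e is the correlation between the transient parts of the two measurements. With e = 0 there is no fall and the rate is 2.5%. With e = 0.3 and n = 92, taking the SD of change as √[2(1 − ρ)]:

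- ρ = 0.7, upper half selected: 0.3 × 0.3 × 0.798 = 0.07 SD, false improvement 14%.
- ρ = 0.9, upper three quarters selected (m = 0.424): 0.3 × 0.1 × 0.424 = 0.01 SD, about 5%.

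Admitting patients on plaque as well would dilute this further.

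**4. Does an arm contrast remove it?** Regression to the mean is shared by comparable arms. Simulating direct selection on the analysed variable (ρ 0.7 or 0.9, upper half or three quarters) with 46 per arm and no effect, the between-arm test of change rejects in 5.0% to 5.4% of trials, against a nominal two-sided 5%.

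**5. Price in precision.** With SD of change s = √[2(1 − ρ)], the standard error is s/√92 = 0.104s for the pooled change and s√(2/46) = 0.209s for the arm contrast, twice as large. The smallest difference detectable with 80% power is 0.58, 0.45 and 0.26 baseline SD for ρ = 0.5, 0.7 and 0.9.

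**The case against.** The best defence is that Aim 3 is largely descriptive and that efficacy belongs to Aim 4. The model text says the time coefficient yields adjusted means at each visit. The Aim 3 research question and hypothesis concern association between contrast dynamics and plaque features. The causal phrase is an expectation, not an analysis rule. The open list of confounders could also admit arm.

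Much of this stands: the descriptive means and the association models are untouched by this point. But the causal reading is not a stray phrase, since the Project Timeline repeats it. Nor does Aim 4 supply the missing control as written: it names no between-arm term and falls back on within-patient comparison.

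A reader might also infer that regression to the mean would usually make a null trial look positive. Selecting every patient in the upper half of the analysed variable, at reliability 0.6 to 0.8, would give false improvement in 69% to 95% of trials, and 22% to 40% if half were so selected. The documents do not support applying those figures here. Nobody is selected on a cut-off in Ktrans or wall area; the rule is "elevated blood markers or arterial plaque on MRI". A known lesion is a location, and where earlier imaging found it, the baseline MRI is already a second measurement.

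Finally, untreated progression would oppose regression to the mean, so even the sign of the net bias is open.

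**Conclusion.** The point holds as a fault of inference. A pooled before-after change in selected patients, with no untreated comparison and no arm term, cannot support attribution to treatment. This does not depend on the bias being large or favourable.

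Size and net direction cannot be fixed from the documents. Regression to the mean acts most directly on serum markers used for selection. There the illustrative false-improvement rate runs from nominal to about 20%, depending mainly on how many patients have plaque. For Ktrans and wall area it may be near nominal. These figures rest on the assumed reliability, cut-off and independence of plaque and marker, and they leave out progression and drift.

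It would be wrong to conclude that a genuine between-arm comparison shares the fault. Regression to the mean does not inflate that contrast if the arms are comparable.

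**What to change.** - In the A # 3 statistical analysis and the A # 4 data analysis, add arm and arm-by-time terms to the planned mixed model and report the time course by arm.
- State that any claim that treatment changed DCE parameters, wall area or serum markers rests on the arm-by-time contrast, and that the pooled time coefficient is descriptive.
- In the A # 3 expected results, remove the closing causal words of "will change in a favorable way over the time course of the study due to institution of treatment".

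This needs wording and two model terms, with no extra patients, scans or visits. The cost is scope and precision: the treatment claim narrows to the increment of the statin regimen over lifestyle modification alone, with about twice the standard error of the pooled change. The effect of lifestyle modification itself stays unidentified. The contrast also still depends on the arms being comparable when allocation follows the last digit of the medical record number (Treatment and Clinical Follow-Up), a limitation to state beside the result.

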## Aims

The purpose of this study is to assess carotid artery MRI plaque characteristics in 100 asymptomatic cancer survivors with history of chest, head and neck radiotherapy (HNXRT) and with subclinical atherosclerosis. Another objective is to analyze plaque changes in the same group after initiation of medical treatment for 18 and 36 months.

The following specific aims (A), research questions (RQ) and hypotheses (H) will be addressed.

A 1: To characterize the plaque constituents including fibrous cap (FC), lipid core and hemorrhage within the carotid plaque by MRI

RQ 1a: What are the predominant plaque constituents?

RQ 1b: Is there a predominance of complex and vulnerable plaque features in the neck arterial vasculature of cancer survivors?

H 1: We hypothesize that there is a predominance of vulnerable plaque in carotid arterial vasculature of HNXRT patients due to the phenomenon of radiation vasculopathy.

A 2: Determine the correlation between plaque inflammation (direct measure by MRI) with serum markers of inflammation through blood tests (hsCRP, LpPLA2, IL-6) and metabolomics

and other tests of cardiac or vascular dysfunction (echocardiography and computerized tomography coronary calcium score studies).

RQ 2: Is there any correlation between the direct and surrogate markers of inflammation?

H 2: We hypothesize that there is a predictable correlation between the direct and surrogate measures of inflammation.

A 3: To assess the longitudinal change in the artery plaque characteristics (inflammation and morphology) with treatment.

RQ 3: Is there a predictable relationship between inflammation (pattern of enhancement-contrast kinetics) and vulnerable features within a plaque?

H 3: We hypothesize that changes in plaque characteristics pre and post treatment would correlate with contrast agent dynamics over time.

A 4: To determine the efficacy of comprehensive treatment (life style modification + statin) versus (life style modification + placebo).

RQ 4: Is one regimen better than the other in cancer survivors with subclinical atherosclerosis?

H 4: We hypothesize that comprehensive treatment (life style modification + statin) would have better inflammation control and favorable plaque modification than life style modification alone as measured by parameters in (A2 & A3).

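### Aim 4 compares two regimens, but the model it reuses targets change over time and names no between-arm contrast

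*Combined protocol and SAP*

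**What the plan says.** The hypothesis is between arms. Under Aims, H 4 expects that the statin-plus-lifestyle regimen "would have better inflammation control and favorable plaque modification than life style modification alone". The Examination Plan Overview splits patients with positive tests into two groups, and Treatment and Clinical Follow-Up allocates them by the last digit of the medical record number.

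Under Specific Aims, the A # 4 data analysis combines the methods of Aims 1 to 3 to study plaque remodelling, "inflammation within the plaque and serum markers of inflammation and compare efficacy of different treatment regimens". It continues: "Each patient will get MRI examinations before and after treatment and therefore patients will serve as their own control". It then names PROC MIXED. It gives no model term, contrast, time point or test of its own.

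The longitudinal model being reused is in the A # 3 statistical analysis, a "random coefficient model with random intercept and slope". Its terms are given as follows: "The independent variables will be the time indicator and other potential confounders that we may need to control". The examples are age, gender, race and body mass index. Its target is also stated: "The interest in this model is the coefficient associated with the time indicator". What that coefficient delivers is an adjusted mean at each visit for the study population, with no mention of arm.

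A second A # 3 model relates vessel wall area to the DCE-MRI parameters, and its slope "is interpreted as a measure of adjusted association between the changes in plaque size and morphology, and DCE-MRI dynamic enhancement parameters".

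The Sample Size section rests on Aims 2 and 3 only. It also describes a lag-1 autoregressive within-subject structure, which differs from the random intercept and slope in A # 3.

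**The concern.** H 4 is true or false according to the difference between arms. The A # 3 longitudinal model, as described, estimates the mean course over visits for all patients together. That mean can move because both regimens work equally well, because only one works, or because of anything else that changes over 36 months. A within-patient comparison removes stable differences between patients, but it does not compare regimens.

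The stake is the study's only treatment comparison. A clear time effect could be taken as support for the statin regimen when the arms do not differ. Conversely, a real arm difference could go unseen if the arms move in opposite directions. H 4 covers several MRI and serum parameters at two follow-up visits. With no contrast written down, the plan does not fix which result answers it.

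**Working it through.** **1. What each reused technique estimates**

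| Source | Estimates | Arm contrast? |
|---|---|---|
| A # 1 | Plaque size and constituents | No |
| A # 2 | Relation of MRI measures to serum, echo and CT measures | No |
| A # 3, longitudinal model | Time coefficient; adjusted mean at each visit | None named |
| A # 3, second model | Slope of plaque size and morphology on DCE-MRI parameters | Target is not an arm difference; predictor list partly lost in the text |

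**2. The plan's own power figure**

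Inputs from Sample Size: three measurements, 92 subjects, effect size f = 0.28, alpha 0.05. For a one-way ANOVA, lambda = k × n × f² = 3 × 92 × 0.28² = 21.64, on 2 and 3 × 91 = 273 degrees of freedom. Power is 0.990, and 92 is the smallest n per level that reaches 0.99. The figure reproduces. Its three levels are visits; it has no arm factor, so it says nothing about Aim 4.

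**3. What a time effect says about H 4**

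Assumptions: 92 analysed patients, 46 per arm (the documents state no ratio), effects in SD of individual change, two-sided alpha 0.05.

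| True change, the two arms | Time effect significant | Arm contrast significant |
|---|---|---|
| 0.3 and 0.3 SD | 81% | 5% |
| 0.4 and 0.4 SD | 97% | 5% |
| 0.5 and 0.5 SD | 99.7% | 5% |
| 0.295 and 0.295 SD | 80% | 5% |
| 0 and 0.59 SD | 78% | 80% |
| 0.3 SD in opposite directions | 4% | 81% |

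The time-effect figures in the first three rows are from a paired t test (noncentrality 0.5 × √92 = 4.80 in the third). The last three rows are simulated change scores. Simulating the three-visit random-intercept-and-slope structure with equal change in both arms gave the same picture: 81–82%, 97% and 99.7% for time, and about 5% for arm-by-time.

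Rows 4 and 5 matter most. For the same average change, the time effect is significant about equally often whether H 4 is false or true.

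**4. Precision of the contrast H 4 needs**

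Difference detectable with 80% power, two-sample t test on change:

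- 46/46: 0.59 SD of change
- 37/55: 0.60 SD (about 95% of splits of 92 fall between 37:55 and 55:37 if odd and even digits are equally likely)
- 40/40 or 36/46: about 0.63 SD

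With baseline adjustment and equal variances at baseline and follow-up, multiply by √((1 + rho)/2). For 46/46, rho = 0.5 gives 0.590 × 0.866 = 0.51 SD, and rho = 0.8 gives 0.590 × 0.949 = 0.56 SD. The documents give no value for rho; this range is assumed.

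95% interval half-widths:

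- Between arms: 1.987 × √(2/46) = 0.41 SD
- Before-after, all 92: 1.986/√92 = 0.21 SD

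**The case against.** The strongest reply is that this is incomplete specification, not a wrong analysis. The sentence naming the time coefficient as the target belongs to Aim 3. For Aim 4 the plan says that regimens will be compared, PROC MIXED accepts a group term, and the list of confounders is open-ended. A reader might infer that the sponsor intends to present the pooled time effect as the Aim 4 result. The documents do not support that: nowhere do they say so, and pooling over arms is inferred from the absence of any arm variable.

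Two other strong readings also fail. Self-control is not the declared rationale for Aim 4: the paragraph labelled as rationale says that treatment combinations have not been studied in this setting, and the self-control sentence may mean only that change from baseline is the response. Nor can anything be said about missing terms in the second A # 3 model, because its predictor list is damaged.

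It is also fair that the rejection rates in step 3 use assumed effects. They show that the estimate does not match the question; they do not predict this trial's result.

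What does not stand is the suggestion that intent is enough. The sentences on the longitudinal model's terms and target are intact. No section supplies the contrast, and the only control the Aim 4 analysis names is the patient's own earlier scan.

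**Conclusion.** The point holds as a gap in the Aim 4 analysis that should be fixed. The intent to compare regimens is stated, but the analysis given, followed as written, yields a before-after change that cannot test H 4. This conclusion comes from the text and does not depend on the assumed effects.

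The precision figures do depend on assumptions. The 0.59 SD figure is a best case: it takes all 92 patients as randomised, evenly split and scanned at follow-up. Only patients with positive tests are randomised, and the documents do not say how many that will be. The 0.51 to 0.56 SD range further needs a baseline/follow-up correlation of 0.5 to 0.8 and equal variances.

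**What to change.** For Aim 4, make these changes:

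- **Model.** Add allocated arm and arm-by-visit to the planned PROC MIXED model, with baseline, 18 and 36 months as responses; if baseline means are constrained equal across arms, omit the arm main effect. Alternatively, use baseline as a covariate with only the follow-up visits as responses. Do not use baseline in both roles.
- **Covariance.** Reconcile the random intercept and slope in A # 3 with the lag-1 autoregressive structure in Sample Size.
- **Estimate.** Report the between-arm difference in change from baseline to 36 months, which Project Timeline makes the end point for final analyses. Give its 95% confidence interval, with patients analysed by allocated arm. Report 18 months as well.
- **Wording.** Replace the self-control sentence, and label pooled or within-arm change as descriptive.
- **Missing data.** Treatment and Clinical Follow-Up and Adverse Event Reporting take patients with treatment side effects out of the study. State that these losses will fall mainly in the statin arm, so the allocated-arm estimate rests on a missing-data assumption unless those patients' scans are still obtained.
- **Power.** State that only Aims 2 and 3 were powered, and give the detectable arm difference for the chosen model with its assumptions.

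As a separate point, the comparator is described as including placebo in Aims (A 4) and as lifestyle or exercise advice alone in H 4, Examination Plan Overview, Treatment and Clinical Follow-Up and A # 4. These passages must be reconciled so that the estimate names what differed between arms.

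The cost is a short paragraph and one or two model terms, with no new measurements unless scans of withdrawn patients are pursued. The between-arm interval is about twice as wide as the before-after one (half-width 0.41 versus 0.21 SD), and Aim 4 must be presented as having limited power.
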